4. OUTCOMES

Primary outcome

- Prevalence of middle-aged women with urinary incontinence.

Secondary outcomes

- Description of UI and related predictors, quality of life, social impact and costs.
- Association between UI and related predictors, quality of life, social impact and costs.

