UI prevalence and symptomatology	Lifestyle factors	
 Unhealthy voiding behavior (Hu and Pierre, 2019) and low physical activity may contribute to UUI onset (Li et al., 2023) Smoking cessation is a general public health measure and has been shown to be weakly associated with improving urgency, frequency and UI (Danforth et al., 2006; Harding et al., 2023) Decrease in fluid intake may improve some symptoms in patients with SUI and idiopathic detrusor overactivity (Swithinbank et al., 2005) Reduction of caffeine intake may reduce symptoms of frequency and urgency (Harding et al., 2023) An association was seen between alcohol consumption and urinary incontinence in middle-aged and older women (Lee & Hirayama, 2012)
	Frequency of urine leakage	To assess the severity of UI among female, we need measuring the “frequency” and “usual amount” of leakage ranged from “moderate” to “strong” (Avery et al., 2004)
	Perceived quantity of urine leakage	
	Type of urine leakage	It is focused on subtypes of urinary incontinence (SUI, UUI and MUI) (Abrams et al., 2003)
	Time of onset of urine leakage	The mean age in which urine leakage begins seems to be lower for SUI compared to MUI and UUI (Thangarajah et al., 2020)

 
I.R.C.C.S. Ospedale San Raffaele
	
STUDY PROTOCOL
	
WUIPS Version n. 1 23.08.2023

---	------------------------------	---

UI quality of life, social impact	General interference with daily life	The measurement of UI should incorporate the impact that the condition may have on quality of life (Avery et al., 2004)
	Interference with specifical activities	
Specifically:
 
 • Physical Activity • Social Relationships • Travel • Emotional Health 
(Monticone et al., 2021; Shumaker et al., 1994)

	Interference with sexual life	Some articles report that UI affects sexual aspects of the individual (Felsted & Supiano, 2019; Marques et al., 2015). According to other studies, sexual activity does not seem to be damaged by UI (Siracusano et al., 2003)
Costs	Work productivity	UI imposes a high economic burden because of work productivity loss (Goren et al., 2014)
	Weekly costs of hygiene care products	UI is associated with substantial routine care “costs” (Subak et al., 2006)

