9.1.1 UI Survey

A survey, written in Italian by the authors, will collect women's socio-demographic, economic and clinical characteristics, based on the variables reported in Table 1. The entire survey is attached in Appendix.

 
I.R.C.C.S. Ospedale San Raffaele
	
STUDY PROTOCOL
	
WUIPS Version n. 1 23.08.2023

---	------------------------------	---

A total of 29 questions will attempt to acquire information about some of the previously defined variables: specifically, 23 questions will be related to socio-demographic and clinical predictors of UI (n. 1-23), one question will be about the onset of the UI symptomatology (n. 35), one question about sexuality (n. 36) and four questions will investigate the direct and indirect costs of UI (n. 37-40). The survey was tested as a pilot on a sample of 13 women aged between 40 and 65 years old and was assessed as suitable for the following aspects: understanding and clarity of the questions, absence of questions that put the participant in difficulty, completion time (which resulted maximum of 5 minutes).

9.1.2 International Consultation of Incontinence Modular Questionnaire Urinary Incontinence Short Form (ICIQ UI-SF)

The International Consultation of Incontinence Modular Questionnaire Urinary Incontinence Short Form (ICIQ UI-SF) is a questionnaire that allows the assessment of the prevalence, frequency, and perceived cause of UI and its impact on everyday life. It is an appropriate scale for estimating national prevalence in representative samples (Bedretdinova et al., 2015).

ICIQ UI-SF was developed and validated in English for the first time by Avery and colleagues in 2004, and then Tubaro and colleagues made an Italian Validation in 2006. This last version will be used in the study.

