- 5. Ho perdite di urina quando sono in movimento e durante l'attività fisica
- 6. Ho perdite di urina quando ho finito di urinare e mi sono rivestita
- 7. Ho perdite di urina senza ragioni particolari
- 8. Ho perdite di urina continuamente

Incontinence Impact Questionnaire-7 (Italian)

Le saremmo grati se rispondesse a queste ultime domande, per comprendere l'influenza sulla qualità di vita delle perdite di urina che ha riscontrato.

NOTA BENE: Se non ha mai riscontrato perdite di urina, le chiediamo di apporre una crocetta sul seguente quadratino e di non rispondere alle domande nella tabella. Grazie per la collaborazione.

- Non ho perdite di urina

Se ha riscontrato perdite di urine, queste perdite hanno influenzato...

	Per nulla	Molto poco	Un po'	Molto
28. La sua capacità di fare le faccende domestiche (cucina, pulizie di casa, lavanderia, ecc.)?	0	1	2	3
29. Le sue attività fisiche ricreative, come camminare, nuotare, o fare	0	1	2	3

altro esercizio?				
30. Le sue attività del tempo libero (andare al cinema, concerti, ecc.)?	0	1	2	3
31. La sua capacità di viaggiare in auto o in autobus per più di 30 minuti da casa?	0	1	2	3
32. La sua partecipazione ad attività sociali fuori casa?	0	1	2	3
33. La sua salute emotiva (nervosismo, depressione, ecc.)?	0	1	2	3
34. I suoi sentimenti di frustrazione?	0	1	2	3

Di seguito le poniamo qualche domanda su insorgenza, evoluzione, impatto della patologia e costi da essa derivanti.

NOTA BENE: Se non ha mai riscontrato perdite di urina, le chiediamo di apporre una crocetta sul seguente quadratino e di non rispondere alle domande successive. Grazie per la collaborazione.

Non ho perdite di urina

35. Da quanto tempo ha delle perdite di urina?

- 1. Da 1 anno o meno
- 2. Da 2-5 anni
- 3. Da 6-10 anni
- 4. Da più di 10 anni

36. Le sue perdite di urina hanno influenzato la sua vita sessuale?

- 1. Per nulla
- 2. Molto poco
- 3. Un po'
- 4. Molto

37. Le sue perdite di urina hanno comportato assenteismo o minore produttività sul posto di lavoro?

- 1. No
- 2. Sì, raramente
- 3. Sì, a volte
- 4. Sì, spesso

38. In media, potrebbe fornire una stima della spesa settimanale che sostiene per l'acquisto di prodotti igienici specifici per le perdite di urina (assorbenti o pannolini, salviettine, detergenti intimi specifici, ecc.)?

- 1. Non acquisto alcun prodotto specifico per le perdite di urina
- 2. Spendono meno di 3 euro a settimana
- 3. Spendono fino a 5 euro a settimana

- 4. Spendò tra i 6 e i 10 euro a settimana

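### Question 36 cannot separate women whose sexual life is unaffected by leakage from women to whom the question does not apply

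*Protocol*

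**What the plan says.** Section 9, Table 1 lists interference with sexual life as a variable under quality of life and social impact. It notes that the literature disagrees: "Some articles report that UI affects sexual aspects of the individual", while in other studies "sexual activity does not seem to be damaged by UI". Section 4 makes this part of the secondary outcomes, which cover both description ("Description of UI and related predictors, quality of life, social impact and costs") and association.

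Section 9.1.1 assigns one survey question to sexuality, number 36. In the Appendix it reads "36. Le sue perdite di urina hanno influenzato la sua vita sessuale" and offers *Per nulla*, *Molto poco*, *Un po'* and *Molto*. It states no recall period and does not ask whether the woman is sexually active.

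The only filter before questions 35 to 40 is for women who have never leaked: "Se non ha mai riscontrato perdite di urina, le chiediamo di apporre una crocetta sul seguente quadratino e di non rispondere alle domande successive". Questions 1 to 23 hold no item on sexual activity or on having a partner.

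Section 9.1.1 also reports a pilot in 13 women, which judged the survey suitable for, among other things, "absence of questions that put the participant in difficulty".

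**The concern.** A woman with leakage who has no sexual activity for unrelated reasons has no answer that says so. She can tick *Per nulla*, and is then recorded like an active woman who is unaffected, or she can leave the item blank, and then looks like a woman who declined to answer. A woman who stopped because of leakage can tick *Molto*, but cannot be told from an active woman who is strongly affected.

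Two things are at stake. The proportion affected has an unclear denominator, which weakens what the study can add on a question where Table 1 says the evidence conflicts. Subgroups that differ in how many women are inactive can also appear to differ in interference, which matters because association is among the secondary outcomes.

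An analysis plan cannot repair this, since the form never collects the distinction. Sections 8 and 16 say data are collected anonymously, and the protocol foresees no return to respondents.

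**Working it through.** The protocol states no figure for question 36, so there is nothing to reproduce. The check has two parts.

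**The form.** The Appendix gives four graded options, one skip (never leaked) and no companion item. Every woman with leakage, active or not, is therefore directed to the same four boxes.

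**Illustration on assumed shares.** The documents give none of these inputs. Among women with leakage, let

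- *p* = proportion of sexually active women affected (assumed 20% to 40%);
- *o* = share inactive for other reasons (assumed 10% to 30%);
- *l* = share inactive because of leakage (assumed 0% to 10%);
- *a* = 1 − *o* − *l* = share active.

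Affected means any answer above *Per nulla*. The two possible targets are

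- all women with leakage: *a·p* + *l*;
- women to whom the item applies: (*a·p* + *l*) / (*a* + *l*).

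*Step 1: nobody inactive because of leakage (l = 0).* The value among women to whom the item applies is then *p*. If the other inactive women tick *Per nulla*, the observed value is (1 − *o*)·*p*; if they leave a blank, it is *p*.

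| p | o | Observed, *Per nulla* ticked | Observed, left blank |
|---|---|---|---|
| 40% | 10% | 0.90 × 0.40 = 36% | 0.36 / 0.90 = 40% |
| 40% | 30% | 0.70 × 0.40 = 28% | 0.28 / 0.70 = 40% |
| 20% | 10% | 0.90 × 0.20 = 18% | 0.18 / 0.90 = 20% |
| 20% | 30% | 0.70 × 0.20 = 14% | 0.14 / 0.70 = 20% |

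The shortfall in the ticked column is *o·p*, from 0.10 × 0.20 = 2 points to 0.30 × 0.40 = 12 points. Two subgroups with the same *p* = 40% but 10% and 30% inactive would show 36% and 28%, an 8-point gap with no difference among active women.

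*Step 2: some women inactive because of leakage.* Take *p* = 40%, *o* = 30%, *l* = 10%, so *a* = 60%. All women with leakage: 0.60 × 0.40 + 0.10 = 34%. Women to whom the item applies: 0.34 / 0.70 = 48.6%.

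| Who answers how | Observed |
|---|---|
| Other inactive tick *Per nulla*; leakage-abstinent tick a higher option | 34% |
| All inactive tick *Per nulla* | 0.60 × 0.40 = 24% |
| All inactive leave a blank | 0.24 / 0.60 = 40% |
| Only other inactive leave a blank | 0.34 / 0.70 = 48.6% |

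The same population yields anything from 24% to 48.6%. The first row equals the all-women target, the last equals the applicable-women target, and the form does not show which row one is in.

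**The case against.** The strongest reply is that *Per nulla* is literally true for a woman inactive for other reasons: leakage has not influenced her sexual life. Section 5(d) aims to describe women with UI, not sexually active women with UI. On that denominator 36% and 28% are correct figures, not diluted ones. This stands, and makes the matter one of denominator and interpretation rather than plain misclassification. It does not remove the problem, because blanks remain uninterpretable and the second proportion cannot be formed at all.

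A reader might infer that women who gave up sexual activity because of leakage are forced into *Per nulla* or a blank, so that the worst affected count as unaffected. The form does not support this. The question concerns the influence of leakage on sexual life, is not limited to currently active women, and *Molto* answers it for them.

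A reader might also infer a definite bias towards no effect, or one that grows with age and menopause. Neither is shown: the direction depends on who ticks what and on the target group, and the protocol has no data on inactivity by age or menopausal status. Table 1 summarises conflicting literature; it states no hypothesis that such a bias would favour.

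The response format is not odd in itself. The IIQ-7 items in the Appendix carry the same four labels, also ask about activities a woman may not pursue, and have no not-applicable box. But the IIQ-7 is a validated scale to be left as it is, whereas question 36 is the researchers' own.

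The pilot does not settle the point. The aspects it reports are clarity, difficulty and completion time, not applicability. If its 13 women leaked at the 25% to 45% that section 11 quotes for most studies of adult women, about 3 to 6 of them (13 × 0.25 = 3.25; 13 × 0.45 = 5.85) would have been directed to question 36.

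**Conclusion.** The point holds in limited form. Question 36 cannot separate unaffected women from women to whom it does not apply, cannot tell a not-applicable blank from a refusal, and cannot identify women who stopped because of leakage. That follows from the form alone.

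The size is not known. If women inactive for other reasons tick *Per nulla*, and nobody is inactive because of leakage, the proportion falls 2 to 12 points below its value among women to whom the item applies. If they leave the item blank, this shortfall need not arise. The figures rest entirely on the assumed shares.

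This is a minor weakness in one item of a secondary outcome, with no bearing on the primary prevalence outcome. It merits action because it is cheap to correct before data collection and cannot be corrected afterwards.

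**What to change.** Add two options to question 36, on paper and in RedCap:

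- not sexually active because of urine leakage, counted as affected;
- not sexually active for other reasons, treated as not applicable.

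Report the proportion affected twice, with the denominator stated each time: among all women with leakage who answer, and among those to whom the item applies. Remaining blanks can then be read as non-response.

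The cost is two tick boxes, a smaller denominator for the second proportion and a slightly more intrusive question. No validated instrument is altered. If forms are already in use, answers from the two layouts should be kept apart for this item.

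### The answer bands of survey question 38 (weekly spend on hygiene products) overlap below 3 euro and leave amounts between 5 and 6 euro without a box

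*Protocol*

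**What the plan says.** Protocol section 4 lists among the secondary outcomes "Description of UI and related predictors, quality of life, social impact and costs", and a further one on association that also includes costs. Table 1 in section 9 places three variables under costs: work productivity, "Weekly costs of hygiene care products", and healthcare resource use. Section 9.1.1 assigns questions 37 to 40 of the survey to direct and indirect costs.

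Of these four, only question 38 asks for money. Its stem reads "potrebbe fornire una stima della spesa settimanale che sostiene", which asks for an estimate of weekly spending. The options are:

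1. "Non acquisto alcun prodotto specifico per le perdite di urina" (buys no specific product)
2. "meno di 3 euro a settimana" (less than 3 euro)
3. "fino a 5 euro a settimana" (up to 5 euro)
4. "tra i 6 e i 10 euro a settimana" (between 6 and 10 euro)
5. more than 10 euro per week

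Questions 24 and 25 tell the respondent to tick one box only. Question 38 carries no such instruction. Nothing elsewhere in the protocol says how option 3 is to be read or where an amount between 5 and 6 euro belongs.

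**The concern.** Closed bands should give each respondent exactly one truthful answer. Here a woman who spends 2 euro a week can truthfully tick option 2 or option 3, and a woman who spends 5.50 euro can tick neither. The limits are written in words, so a symbol lost in reading the PDF does not explain it.

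What is at stake is one descriptive cost variable. Low spenders may divide between two boxes according to how they read the list, so the counts in options 2 and 3 would partly reflect wording and not spending. Patients and caregivers answer on paper (section 8), where no software stops a double tick. The data are anonymous (sections 8 and 16), so an unclear answer cannot be queried later.

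**Working it through.** **Inputs.** All come from question 38 in the Appendix. With x the weekly spend in euro, the four spending options read literally are:

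- Option 2: 0 < x < 3
- Option 3: 0 < x ≤ 5 (no lower limit printed)
- Option 4: 6 ≤ x ≤ 10
- Option 5: x > 10

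The plan gives no figure of its own to reproduce.

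**Step 1: count the options that contain each amount.** For every cent from 0.01 to 15.00 euro (1,500 amounts):

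| Options that fit | Amounts | Range |
|---|---|---|
| two (2 and 3) | 299 | 0.01 to 2.99 |
| none | 99 | 5.01 to 5.99 |
| exactly one | 1,102 | the rest |

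Check: 299 + 99 + 1,102 = 1,500. These are counts of possible amounts, not of women; the protocol gives no distribution of spending.

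**Step 2: repeat in whole euros.** Amounts of 1 and 2 fit options 2 and 3. Amounts of 3, 4 and 5 fit option 3 only, 6 to 10 fit option 4 only, and 11 and above fit option 5 only. The gap disappears and the overlap remains.

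**Step 3: compare with other items on the form.** Question 22, on daily water intake, has a band of the same kind but prints its lower limit (above one litre, up to one and a half). Question 19, on cigarettes, also gives both limits for its middle bands. The missing lower limit in question 38 therefore looks like a drafting slip and not a convention of the form.

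**Step 4: gauge the effect if someone used midpoints.** The protocol does not say that this will be done, so this is an illustration only. The midpoint of option 3 is (0 + 5)/2 = 2.5 euro or (3 + 5)/2 = 4.0 euro, depending on the reading. Assume one fifth of women in each option, values 0, 1.5 and 8 for options 1, 2 and 4, and a value T for the open top option:

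mean = (0 + 1.5 + midpoint of option 3 + 8 + T)/5

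| T (assumed) | Option 3 = 2.5 | Option 3 = 4.0 |
|---|---|---|
| 12 | 4.8 | 5.1 |
| 15 | 5.4 | 5.7 |
| 20 | 6.4 | 6.7 |

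The reading of option 3 moves the mean by 1.5/5 = 0.3 euro per week. The choice of T moves it by up to (20 − 12)/5 = 1.6 euro. The open top option would therefore matter more than the overlap.

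**Step 5: check the reworded bands.** With less than 3, from 3 to 5, more than 5 up to 10, and more than 10, all 1,500 amounts fall in exactly one band.

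**The case against.** The case for leaving the item alone has several parts.

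- **Natural reading.** In a rising list with a less-than-3 option directly above, most women will probably take option 3 as 3 to 5 euro. This is fair and is the main reason to expect a small effect. It does not make the wording exclusive.
- **Whole euros.** The stem asks for an average estimate, for which whole euros are the natural unit, and question 35 uses whole-number limits in years in the same way. This largely disposes of the gap, but not of the overlap at 1 and 2 euro.
- **The pilot.** Section 9.1.1 reports that 13 women tested the survey and that it was judged clear. But women without leakage are told to skip questions 35 to 40, and the protocol does not say how many of the 13 had leakage. If the prevalences cited in section 11 applied, 13 × 10.2% = 1.3 to 13 × 45% = 5.9, so about 1 to 6 women would have answered question 38. A test of clarity is also not a test of whether the bands are exclusive.

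A reader might also infer more than the documents support:

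- **That the cost outcome as a whole fails.** Question 38 feeds one of three cost variables in Table 1. Questions 37, 39 and 40 are unaffected.
- **That a mean cost becomes ambiguous.** Section 13 plans means for quantitative variables but does not say that question 38 is one. The open top option would rule out an unambiguous mean even with perfect bands.
- **That the error is 60%, or 78 euro a year, per woman in option 3.** These figures come from 4.0/2.5 = 1.6 and 1.5 × 52 = 78. They compare two extreme codings; the lower one spreads the women in option 3 evenly over 0 to 5 euro, as if option 2 drew none of them. They are not an expected error.
- **That the answers cannot be repaired once collected.** Pooling options 2 and 3 gives a category that is true under either reading. What is lost is the distinction at 3 euro. Pooling does not place women who spend between 5 and 6 euro.

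**Conclusion.** The point holds as a minor defect of one author-built survey item. As worded, the bands of question 38 are neither mutually exclusive nor exhaustive, and nothing else in the protocol resolves this. The split between options 2 and 3 cannot be relied on, and exact amounts between 5 and 6 euro have no home.

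The effect is probably small. That judgement assumes that most respondents read the list as ascending and round to whole euros, which the protocol gives no data to confirm. The primary outcome, prevalence, is not affected. The correction is worth making because it is specific, costs little, and concerns the only euro amount the study collects.

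**What to change.** Reword the options of question 38, on paper and in REDCap, as: no specific product bought; less than 3 euro; from 3 to 5 euro; more than 5 and up to 10 euro; more than 10 euro per week. Add the single-tick instruction already used in questions 24 and 25. The survey was written by the researchers, so no validated questionnaire is altered.

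The cost is two changed option lines, one added instruction, and a revised form to be notified to the Ethics Committee, since section 14 requires new versions to be shared with it.

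If forms are already in use, pool options 2 and 3 as up to 5 euro, report the item by category (none, up to 5, 6 to 10, more than 10), and state the ambiguity. This gives up some resolution at the low end and leaves amounts between 5 and 6 euro unplaced.

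The rewording does not close the top band. Any later conversion to a mean would still need a stated value for it.
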